15.6 Sample Size and Randomization

We will base sample size calculations on the comparison of the probability of correctly responding to the two survey questions between subjects at the intervention versus control sites with a design effect correction to accommodate the potential correlation of responses within sites [44]. That is, we will inflate the sample sizes resulting from standard sample calculations for the comparison of two proportions by the design effect, $1 + (n-1)*\rho$, where n is the sample size per site and ρ is the intraclass correlation coefficient of the primary binary response[45]. We are interested in detecting an alternative where the probability of the primary response increases from 0.5 in the control sites to 0.75 in the intervention sites. Standard power calculations for chi-square tests to compare two proportions [45] show that tests based on a total sample size of 116 would have power 0.8 to detect the alternative of interest. Since our study design involves 8 clusters (four sites measured in two time periods), our initial design would include 15 subjects measured in each site at each time. Preliminary data indicate that the intraclass correlation coefficient of the primary response is quite low within sites; the estimated intraclass correlation coefficient was less than 0.01. This estimate produces a design effect of 1.14 and we inflate the required number of subjects per site and time to 17 for a total sample size of 136.

Randomization: At baseline, this study will randomize two sites to the intervention and two sites to serve as controls. There are six possible assignments of two intervention and control sites in our study and we will generate a uniform (0,1) random number to select one of them.

16 DATA COLLECTION, RETENTION AND MONITORING

16.1 Data Collection Instruments

The Investigator will prepare and maintain adequate and accurate source documents designed to record all observations and other pertinent data for each subject treated with the study drug.

Study personnel at each site will enter data from source documents corresponding to a subject's visit into the protocol-specific electronic Case Report Form (eCRF) OR paper CRF when the information corresponding to that visit is available. Onsite CRCs will have access to a UCSF hosted REDCaP database (see <https://redcap.ucsf.edu/index.php>). The database will be partitioned by each site to maintain the confidentiality of site specific participants.

For eCRFs: If a correction is required for an eCRF, the time and date stamps track the person entering or updating eCRF data and creates an electronic audit trail. Paper-mode CRFs will be used only for PROMs which will be entered into the REDCaP database. *For paper CRFs:* If a correction is made on a CRF, the study staff member will line through the incorrect data, write in the correct data and initial and date the change.

The Investigator is responsible for all information collected on subjects enrolled in this study. All data collected during the course of this study must be reviewed and verified for completeness and accuracy by the Investigator. A copy of the CRF will remain at the Investigator's site at the completion of the study.

16.2 Data Management Procedures

The data will be entered into a validated database. The Data Management group will be responsible for data processing, in accordance with procedural documentation. Database lock will occur once quality assurance procedures have been completed.

All procedures for the handling and analysis of data will be conducted using good computing practices meeting FDA guidelines for the handling and analysis of data for clinical trials.

16.3 Data Quality Control and Reporting

After data have been entered into the study database, a system of computerized data validation checks will be implemented and applied to the database on a regular basis. *For EDC studies:* Queries are entered, tracked, and resolved through the EDC system directly. *For paper studies:* Query reports (Data Clarification Requests) pertaining to data omissions and discrepancies will be forwarded to the Investigators and study monitors for resolution. The study database will be updated in accordance with the resolved queries. All changes to the study database will be documented.

16.4 Archival of Data

The database is safeguarded against unauthorized access by established security procedures; appropriate backup copies of the database and related software files will be maintained. Databases are backed up by the database administrator in conjunction with any updates or changes to the database.

At critical junctures of the protocol (e.g., production of interim reports and final reports), data for analysis is locked and cleaned per established procedures.

All ICF, HIPAA, and/or paper-mode PROMs will be digitally archived and attached to the relevant section in the REDCaP database.

16.5 Availability and Retention of Investigational Records

The Investigator must make study data accessible to the monitor, other authorized representatives of the Sponsor (or designee), IRB/IEC, and Regulatory Agency (e.g., FDA) inspectors upon request. A file for each subject must be maintained that includes the signed Informed Consent, HIPAA Authorization and Assent Form and copies of all source documentation related to that subject. The Investigator must ensure the reliability and availability of source documents from which the information on the CRF was derived.

All study documents (patient files, signed informed consent forms, copies of CRFs, Study File Notebook, etc.) must be kept secured for a period of two years following marketing of the investigational product or for two years after centers have been notified that the IND has been discontinued. There may be other circumstances for which the Sponsor is required to maintain study records and, therefore, the Sponsor should be contacted prior to removing study records for any reason.

16.6 Monitoring

Not applicable

16.7 Subject Confidentiality

No raw / identifiable data from the study will be shared with the study sponsor, the Department of Defense U.S. Army Medical Research Transformative Impact Award group.

17 ADMINISTRATIVE, ETHICAL, REGULATORY CONSIDERATIONS

The study will be conducted according to the Declaration of Helsinki, Protection of Human Volunteers (21 CFR 50), Institutional Review Boards (21 CFR 56), and Obligations of Clinical Investigators (21 CFR 312).

To maintain confidentiality, all laboratory specimens, evaluation forms, reports and other records will be identified by a coded number and initials only. All study records will be kept in a locked file cabinet and code sheets linking a patient's name to a patient identification number will be stored separately in another locked file cabinet. Clinical information will not be released without written permission of the subject, except as necessary for monitoring by the FDA. The Investigator must also comply with all applicable privacy regulations (e.g., Health Insurance Portability and Accountability Act of 1996, EU Data Protection Directive 95/46/EC).

17.1 Protocol Amendments

Protocol amendments cannot be implemented without prior written IRB/IEC approval except as necessary to eliminate immediate safety hazards to patients. A protocol amendment intended to eliminate an apparent immediate hazard to patients may be implemented immediately, provided the IRBs are notified within five working days.

17.2 Institutional Review Boards and Independent Ethics Committees

The protocol and consent form will be reviewed and approved by the IRB/IEC of each participating center prior to study initiation. Serious adverse experiences regardless of causality will be reported to the IRB/IEC in accordance with the standard operating procedures and policies of the IRB/IEC, and the Investigator will keep the IRB/IEC informed as to the progress of the study. The Investigator will obtain assurance of IRB/IEC compliance with regulations.

Any documents that the IRB/IEC may need to fulfill its responsibilities (such as protocol, protocol amendments, Investigator's Brochure, consent forms, information concerning patient recruitment, payment or compensation procedures, or other pertinent information) will be submitted to the IRB/IEC. The IRB/IECs written unconditional approval of the study protocol and the informed consent form will be in the possession of the Investigator before the study is initiated. The IRB/IECs unconditional approval statement will be transmitted by the Investigator to the Sponsor or designee prior to the shipment of study supplies to the site. This approval must refer to the study by exact protocol title and number and should identify the documents reviewed and the date of review.

Protocol and/or informed consent modifications or changes may not be initiated without prior written IRB/IEC approval except when necessary to eliminate immediate hazards to the patients or when the change(s) involves only logistical or administrative aspects of the study. Such modifications will be submitted to the IRB/IEC and written verification that the modification was submitted and subsequently approved should be obtained.

The IRB/IEC must be informed of revisions to other documents originally submitted for review; serious and/or unexpected adverse experiences occurring during the study in accordance with the standard operating procedures and policies of the IRB; new information that may affect adversely the safety of the patients of the conduct of the study; an annual update and/or request for re-approval; and when the study has been completed.

17.3 Informed Consent Form

Informed consent will be obtained in accordance with the Declaration of Helsinki, ICH GCP, US Code of Federal Regulations for Protection of Human Subjects (21 CFR 50.25[a,b], CFR 50.27, and CFR Part 56, Subpart A), the Health Insurance Portability and Accountability Act (HIPAA, if applicable), and local regulations.

The Investigator will prepare the informed consent form, assent and HIPAA authorization and provide the documents to the Sponsor or designee for approval prior to submission to the IRB/IEC. The consent form generated by the Investigator must be acceptable to the Sponsor and be approved by the IRB/IEC. The written consent document will embody the elements of informed consent as described in the International Conference on Harmonisation and will also comply with local regulations. The Investigator will send an IRB/IEC-approved copy of the Informed Consent Form to the Sponsor (or designee) for the study file.

A properly executed, written, informed consent will be obtained from each subject prior to entering the subject into the trial. Information should be given in both oral and written form and subjects (or their legal representatives) must be given ample opportunity to inquire about details of the study. If appropriate and required by the local IRB/IEC, assent from the subject will also be obtained. If a subject is unable to sign the informed consent form (ICF) and the HIPAA authorization, a legal representative may sign for the subject. A copy of the signed consent form

(and assent) will be given to the subject or legal representative of the subject and the original will be maintained with the subject's records.

17.4 Publications

The preparation and submittal for publication of manuscripts containing the study results shall be in accordance with a process determined by mutual written agreement among the study Sponsor and participating institutions. The publication or presentation of any study results shall comply with all applicable privacy laws, including, but not limited to, the Health Insurance Portability and Accountability Act of 1996.

17.5 Investigator Responsibilities

By signing the Agreement of Investigator form, the Investigator agrees to:

1. Conduct the study in accordance with the protocol and only make changes after notifying the Sponsor (or designee), except when to protect the safety, rights or welfare of subjects.
2. Personally conduct or supervise the study (or investigation).
3. Ensure that the requirements relating to obtaining informed consent and IRB review and approval meet federal guidelines, as stated in § 21 CFR, parts 50 and 56.
4. Report to the Sponsor or designee any AEs that occur in the course of the study, in accordance with §21 CFR 312.64.
5. Ensure that all associates, colleagues and employees assisting in the conduct of the study are informed about their obligations in meeting the above commitments.
6. Maintain adequate and accurate records in accordance with §21 CFR 312.62 and to make those records available for inspection with the Sponsor (or designee).
7. Ensure that an IRB that complies with the requirements of §21 CFR part 56 will be responsible for initial and continuing review and approval of the clinical study.
8. Promptly report to the IRB and the Sponsor (or designee) all changes in the research activity and all unanticipated problems involving risks to subjects or others (to include amendments and IND safety reports).
9. Seek IRB approval before any changes are made in the research study, except when necessary to eliminate hazards to the patients/subjects.
10. Comply with all other requirements regarding the obligations of clinical investigators and all other pertinent requirements listed in § 21 CFR part 312.

19 FIGURES AND TABLES

19.1 Figure 1. Decision Support Intervention Study Schematic

***DQI pre-visit is the primary outcome**

19.2 Table 1. DSI Trial - Schedule of Events¹

Intervention Arm	Usual Care Arm

Screen and Recruit
 
 1. Post “Diagnosis Confirmation” phone call by the physician or the clinical nurse, the onsite CRC will contact the patient about their eligibility and interest in participating in the decision support study. If they obtain verbal permission, will send them a packet of information with the Informed Consent (IC), HIPAA and T1 surveys via FedEx 2. Onsite CRC enters REDCaP CRFs: 
 a. Subject Identifiers b. Eligibility for Study 3. Onsite CRC notifies UCSF data coordinating center to send FedEx package – this could be done by call or e-mail. 	
Screen and Recruit
 
 1. Post “Diagnosis Confirmation” phone call by the physician or the clinical nurse, the onsite CRC will contact the patient about their eligibility and interest in participating in the decision support study and obtain verbal permission to send them a packet of information with the Informed Consent, HIPAA and T1 surveys via FedEx 2. Onsite CRC enters REDCaP CRFs: 
 a. Subject Identifiers b. Eligibility for Study 
Onsite CRC notifies UCSF data coordinating center to send FedEx package – this could be done by call or e-mail.

Enters Decision Support Coaching Study	

T1: Obtain Informed Consent and HIPAA² Enter into REDCaP CRFs:
 
 1. Study Biopsy Results 2. Appointment Information 	
T1: Obtain Informed Consent and HIPAA – Enter into REDCaP Enter into REDCaP CRFs:
 
 1. Study Biopsy Results 2. Appointment Information

T1: Administer T1 surveys - paper or web-mode option Enter into REDCaP CRF:
	
T1: Administer T1 surveys – paper or web-mode option Enter into REDCaP CRF:

¹ Color grid for distribution of tasks associated with the study timed events:

Onsite Coordinator task
UCSF Data coordinating Center task

² If patient is recruited by phone by the onsite CRC, they will notify UCSF to send the paper ICF and HIPAA. The UCSF Data coordinating center will send paper regulatory documents to patient via FedEx. Patient signs and returns signed regulatory forms to UCSF via FedEx. UCSF CRC will scan ICF and HIPAA and attaches into REDCaP database. UCSF CRC will push e-mail to the onsite CRC to notify her/him that patient has consented. UCSF CRC will insure that both the site and the participant have a paper copy of the signed ICF and HIPAA. Upon receipt of a fully executed signed ICF and HIPAA form, the onsite CRC will enter information about the biopsy and the upcoming doctor appointment into REDCaP so the coach can begin the contact and coaching parts of the intervention.

Intervention Arm	Usual Care Arm
1. Consent and HIPAA Forms – UCSF to provide copies to site	1. Consent and HIPAA Forms – UCSF to provide copies to site
T2: Onsite CRC completes the following REDCaP CRFs: 1. Coach Contact Preferences This completes the onsite CRC referral to the coach	
Coach contacts patient and schedules coaching call	
Coach emails patient: decision aid (DA) link and PDF	
Coach calls patient: reviews DA and lists questions	
Coach emails CRC: patient question list	
Patient arrives at practice for consult visit with Urologist	
T3: CRC gives question list printout to patient (separately) and to MD	
T3: Patient completes T3 surveys before visit	T3: Patient completes T3 surveys before visit
Patient appointment with Urologist	
T4: Patient completes T4 surveys after visit	T4: Patient completes T4 surveys after visit
Patient leaves practice	
UCSF research staff call first 3 patients at each site for qualitative debrief	UCSF research staff call first 3 patients at each site for qualitative debrief
Before Treatment Commences	
T5: Patient completes T5 surveys	T5: Patient completes T5 surveys
Patient enters CaPSURE™ cohort	
Patient opts for Participation in the Diet & Lifestyle Sub-study of CaPSURE™	

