5 CRITERIA FOR EVALUATION

5.1 Primary Efficacy Endpoint

The primary endpoint is the proportion of patients who respond accurately to two survey items assessing whether they are more likely to die of prostate cancer or other causes (other causes are more likely); and whether waiting three months to make a treatment decision will affect their survival a lot; somewhat; or a little or not at all (a little or not at all is the correct answer).

Knowledge of these key facts is an important endpoint because patients often associate the word cancer with high mortality risks, and with urgency to act. Patients also often associate more invasive treatment with greater benefit.

In the case of early-stage, low-risk prostate cancer, patients should recognize that early-stage prostate cancer patients are more likely to die of other causes than prostate cancer; and that most can safely take three months to make decisions. This knowledge opens patients up to consideration of active surveillance along with surgery and radiation therapies.

Our intervention aims to educate patients about their (low) mortality risk and the time available for decision-making after their cancer diagnosis **before** they see their urologist for primary treatment counseling. Therefore, we will assess this endpoint just prior to the first urology appointment after a biopsy confirms early-stage low-risk cancer, and compare the usual care results to the intervention arm.

In preliminary studies at an academic medical center with highly educated patients, our intervention increased the proportion of patients responding accurately from 69% to 88%. Meanwhile, at our community sites, 52% of usual care patients responded accurately. We hypothesize that in our randomized controlled trial, we will see over 75% of patients respond accurately in the intervention arm, versus 50% in the usual care arm.

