8.3 Decision Support Intervention

Participants randomly assigned to the Intervention will receive access to our decision aid, developed following the International Patient Decision Aids Standards with the input of patients, family members, physicians, nurses, clinic staff, decision scientists, and clinical researchers [1]. After reviewing the decision aid, either via a secure website or a PDF file emailed to them (whichever is most convenient for them), patients will speak with a trained coach. The coach will review the decision aid screen by screen, or page by page, and write down any questions that the patient voices about the contents of the decision aid. The coach will then review the decision aid help text to address questions that are covered there, and save the remaining questions for the attention of the attending urologist at the upcoming visit. Specifically, the coach will save a word-processed document with the patient’s questions for the physician, and send that file to the site study coordinator, who will print copies for the patient, family, and physician and make those copies available to all parties at the time of the clinic visit. Our surveys will also assess what other decision or communication aids the patient may have accessed on their own prior to the visit.

Our decision aid incorporates the following estimates:

- Survival and quality of life outcomes from the CaPSURE outcomes database for patients who underwent active surveillance, surgery, or radiation.

- Risk of reclassification (“upstaging” or “upgrading”) based on demographic, clinical, and pathologic parameters using a model developed at UCSF and tested using UCSF and CaPSURE data.

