10.4 Contact 3 DSI Coaching (intervention arm only)

Includes: Student coach calls patient and conducts intervention interview, reviewing each screen of the decision aid, typing up patient questions for the doctor, and referring the patient to help text about the decision aid content. Student coach then sends question list to site coordinator to be printed and given to physician at the time of the appointment.

The student health coach will upload to REDCaP before the visit with the urologist.

- a. A summary **Question List (QL) form** includes the following areas of concern generated by the participant and coach using the PCa SCOPED model [37]:
 - i. Situation – clarifying facts about my condition
 - ii. Choices (treatment) – Which options are available
 - iii. Objectives – Clarifying my goals and priorities
 - iv. People – Clarifying roles and responsibilities
 - v. Evaluation – Clarifying how my choices affect my objectives
 - vi. Decisions – Clarifying which choice is best and next steps
- b. Complete and upload the **Prostate Cancer SCOPED model form**

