10.5 Contact 4 Immediately Upon Arrival at Clinic for Urologist Consultation Visit

Includes: Immediately upon arrival, patient should fill out Time 2 surveys – e.g. on tablet or at a kiosk or on paper. These will include Decision Quality Instrument [38], Max PC [39, 40], DSE [35], Control Preferences Scale [34], Choice Predisposition [35], and Reclassification Risk Understanding. Clinic staff or site study coordinator should print question list and give copies to the patient/family and attending physician for use during the medical visit.

1. Print the QL and PCa SCOPED forms for review by the urologist.

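### Table 1 gives intervention men their question list before the T3 survey that holds the primary items, section 10.5 puts the survey first, and no rule says materials are put away

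*Combined protocol and SAP*

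**What the plan says.** **Endpoint and timing.** Section 5.1 defines the primary endpoint as correct answers to two knowledge items and says "we will assess this endpoint just prior to the first urology appointment". The note to Figure 1 identifies the pre-visit Decision Quality Instrument (DQI) as the primary outcome, and Table 2 places that instrument at T3.

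**Table 1 (section 19.2).** The intervention column runs in this order: "Patient arrives at practice for consult visit with Urologist"; then "T3: CRC gives question list printout to patient (separately) and to MD"; then "T3: Patient completes T3 surveys before visit"; then the appointment and the T4 surveys. The usual care column has the T3 survey row but no list row.

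**Section 10.5.** The first instruction is "Immediately upon arrival, patient should fill out Time 2 surveys". After naming the instruments, the section says that clinic staff or the coordinator "should print question list and give copies to the patient/family and attending physician for use during the medical visit".

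**Section 8.3.** The coordinator is to print copies and "make those copies available to all parties at the time of the clinic visit". The order relative to the survey is not given.

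No section says whether the question list, the decision aid or clinic brochures may be consulted while T3 is answered.

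**The concern.** The primary endpoint is meant to capture what men know before the consultation. Clinic staff are not blinded, and section 8.2 answers this by noting that the primary outcome is determined before the consultation. Sequence at the clinic visit is thus one of the plan's own safeguards, and its two descriptions of that sequence disagree at the moment of primary measurement.

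If coordinators work down Table 1, men in one arm answer the knowledge items with a sheet from their coaching call in hand, and men in the other arm have no counterpart. A sheet that brings the call back to mind could help a man recall what the decision aid said. Part of any arm difference would then be aided recall at measurement. T3 also carries decision self-efficacy, prostate cancer anxiety and reclassification risk understanding, so these would be answered under the same unequal conditions. With four sites, practice could also differ from site to site depending on which section the coordinator follows.

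**Working it through.** The point turns on order and content, so the main check sets the passages side by side.

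**1. Are the primary items in the T3 survey?** Section 5.1 does not name the instrument. The Figure 1 note (pre-visit DQI) and Table 2 (DQI at T3 and T4) together place them there. Section 10.5 labels the arrival surveys Time 2, and section 10.6 uses the same label for the post-visit surveys. The arrival set in 10.5 must therefore be matched to T3 by its content and timing.

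**2. What order does each place give?**
- Table 1, intervention: arrival, list, T3 survey, appointment.
- Table 1, usual care: T3 survey, appointment.
- Section 10.5: T3 survey on arrival, then list, for use in the visit.
- Section 8.3: list at the visit, order unstated.

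Table 1 conveys order only by row position, and both rows carry the same T3 tag. The neighbouring rows, from coach contact to leaving the practice, are chronological, so a coordinator would naturally read these two as a sequence as well.

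**3. What is on the list?** Under section 8.3 the coach deals with questions that the help text covers and saves the rest for the urologist. Section 10.4 groups the form under six headings, one of them "clarifying facts about my condition". That phrase is a category label and does not show that facts are written there. No section says that the list states either correct answer.

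**4. What else does the man hold?** By section 8.4 he has the URL and a PDF of the decision aid, or a paper copy under Appendix B. The aid tabulates prostate cancer deaths by initial approach, which bears on the first knowledge item more directly than a sheet of questions does. Usual care men may hold clinic brochures (section 8.3.1). Reordering Table 1 alone would therefore leave a route to answering with materials open.

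**5. Can the effect be sized?** Not from the documents, which give no figure for the effect of holding the list. The plan's sample size does not depend on this point, but it supplies the scale:
- Per arm, for 0.50 against 0.75 with power 0.80 and two-sided alpha 0.05 (alpha is assumed; section 15.6 states none): [1.96·√(2×0.625×0.375) + 0.8416·√(0.50×0.50 + 0.75×0.25)]² / 0.25² = 57.7, rounded up to 58. The total is 116, as stated.
- Design effect 1 + (15−1)×0.01 = 1.14; 15×1.14 = 17.1, taken as 17; 8×17 = 136, as stated, or 68 per arm.

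*Illustration only.* Suppose that the list alone raised correct answers by b, that the intervention had no other effect, that 50% of controls were correct, and that clustering is ignored. With SE = √{[0.25 + (0.5+b)(0.5−b)]/68}, the two-sided rejection probability is P(Z > 1.96 − b/SE) + P(Z < −1.96 − b/SE):
- b = 0.02: 0.042 + 0.014 = 0.056
- b = 0.05: SE = 0.0855, b/SE = 0.585; 0.0845 + 0.0055 = 0.090
- b = 0.10: 0.217 + 0.001 = 0.218

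A shift of 5 points would be 5/25, one fifth of the planned difference. The values of b are assumptions with no basis in the documents, so these results show sensitivity and do not estimate bias.

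**The case against.** The strongest reply has four parts.

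- **The list holds questions.** It records what the man still wants to ask, and he produced it himself during the call. It might even signal doubt. This stands. A reader might infer that intervention men can look up the answers, or that any effect must favour the intervention. The documents support neither inference. The most that can be said is that a cue, if there is one, more plausibly helps than hurts.
- **The list is part of the intervention.** The trial compares the whole package with usual care, so the list is not contamination between arms. This stands too. The issue is narrower: whether pre-visit knowledge is measured under the same conditions in both arms.
- **Section 10.5 already settles the order.** It does so only in part. It puts the survey on arrival and ties the list to the visit, but it never says that the list is held back until the survey is collected. Section 10.6 points readers to the Schedule of Events for procedures and responsibilities, so coordinators may well work from Table 1.
- **Holding the list back has a cost.** Table 2's total row puts T3 at 31 minutes, and section 10.5 wants forms printed for the urologist's review. This is fair for the urologist's copy, which cannot affect the patient's answers, so that copy need not wait.

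**Conclusion.** The conflict between Table 1 and section 10.5 is real and falls at the primary assessment, in one arm only. Neither the presence nor the size of any bias is shown. The list is a possible written cue of unknown size, most plausibly favouring the intervention. A reader might take the illustrative 22% rejection rate as the trial's false positive risk. The documents do not support that: it needs a 10-point gain from a sheet of the man's own open questions while the decision aid and coaching teach nothing.

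The conclusion rests on two readings: that row position in Table 1 means order, and that the two knowledge items sit in the T3 DQI. Grade: minor, a free improvement. It is worth making because it gives sites one order and removes an avoidable objection to a positive primary result.

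**What to change.** 1. Reorder the intervention column of Table 1 to agree with section 10.5. In both arms the T3 survey is completed and collected before the patient (and family) receives a copy of the question list.
2. Add to section 10.5 that T3 is answered in both arms without study or clinic materials in hand, naming the question list, the decision aid (PDF, paper or online) and brochures. Reordering alone does not deal with the decision aid that intervention men already have.
3. Allow the urologist's copy to be delivered at any time before the visit, so that review time is not lost.
4. While editing, use T3 in section 10.5 so that the text and Tables 1 and 2 refer to the same assessment.

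The cost is two table rows exchanged, a sentence or two in section 10.5, and a brief request by the coordinator at arrival. No part of the intervention is removed, since patient and urologist still have the list for the consultation. The sample size and analysis do not change.
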